## 2 Methods

### 2.1 Trial overview, ethical consideration, and patient recruitment

This study is an ongoing, single-center, cross-sectional observational clinical trial. The subjects were selected for observation and subsequent analysis for key biomarkers such as blood glucose, Urine Albumin-to-Creatinine Ratio(UACR), and renal function. Blood, urine, feces, and moss on the tongue samples were collected from the subjects and stored for subsequent analysis. The study protocol was approved by the Ethics Committee of the First Affiliated Hospital of Hunan University of Traditional Chinese Medicine in accordance with the relevant ethical standards. The study is currently being conducted at the First Affiliated Hospital of Hunan University of Traditional Chinese Medicine and involves four groups of participants: type 2 diabetic kidney disease (DKD), type 2 diabetes mellitus (T2DM), chronic kidney disease (CKD), and healthy human. Subjects will be recruited from inpatients or outpatients of the Department of Endocrinology and the Department of Nephrology of the First Affiliated Hospital of Hunan University of Traditional Chinese Medicine. Additionally, healthy human subjects will be recruited from the general public through printed advertisements, invitations, etc. The total number of individuals proposed to be recruited in the four groups is 720.

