### 2.2 Study outcomes

**Primary outcome:** By employing a combination of microbiomic and metabolomic technologies, we conducted a comprehensive analysis of the intestinal flora and serum metabolic profiles associated with DKD. This approach enabled us to identify potential enterogenous disease markers of DKD and to investigate the metabolic profiles that may be linked to disease progression.

**Secondary outcome:** The objective of this study is to analyze the interaction between intestinal flora and intestinal-derived metabolites in the disease process of DKD. Additionally, the aim is to provide new disease diagnostic strategies and progression risk assessment indicators for diabetic nephropathy, which can be applied to early identification, precise diagnosis, and prognosis of the disease.

**Exploratory outcomes :** In accordance with the test results, each group will select four to six remaining fecal samples as the donor source for allogeneic fecal bacteria transplantation. Subsequently, the correlation between intestinal flora and enteric metabolites in diabetic nephropathy will be investigated through the method of human-mouse allogeneic flora transplantation.

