#### 2.4.2 Outcome Measures

Indicators of safety: Physical examination (including general condition, blood pressure, heart rate, heart rhythm, body temperature, respiratory rate, etc.) was

performed before taking the samples to assess the basic condition of the subjects.

**Primary Outcome Measures :** Urine Albumin-to-Creatinine Ratio(UACR), Estimated Glomerular Filtration Rate(eGFR),blood urea nitrogen(BUN), serum creatinine(Scr), fasting blood glucose(FBG), Glycosylated Hemoglobin, Type A1C(HbA1c), glucosylated serum protein(GSP) , etc. Test data were obtained from test results conducted within one month of enrollment for the purpose of evaluation.

**Secondary Outcome Measures:** 16S ribosomal DNA(16S rDNA) identification, metagenomic Next Generation Sequencing, Non-targeted and targeted Metabolomics technology detection , etc.

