## 2.5 Data analysis

SPSS 26.0 will be applied for statistical analysis of clinical indicators. Data that exhibited a normal distribution were expressed as the mean  $\pm$  standard deviation(  $x \pm s$ ), and an independent samples t-test was employed for comparison between two groups. Data that did not conform to a normal distribution were expressed as the median and interquartile spacing [M(IQP)], and a Mann-Whitney rank-sum test (U test) was used for comparison between two groups. In the case of count data, these were expressed as frequencies or percentages. In the event of unordered categorical count data, comparisons between two groups were performed using either the four-cell table or the column table  $c^2$  test. The Pearson  $c^2$  test or Fisher's exact probability method was employed in accordance with the sample size and the size of the theoretical frequency. In the case of ordered categorical count data, comparisons between two groups were performed using the U test. A two-sided test was employed for the normality test and variance chi-square test, with an alpha level of 0.1. This resulted in the rejection of the original hypothesis, indicating that the data are not normally distributed or that there is no significant variance. For other significance tests, an alpha level of 0.05 was used, leading to the rejection of the original hypothesis and the conclusion that the difference is statistically significant.

An integrated correlation analysis will be performed using a variety of analytical techniques, including intestinal flora species diversity analysis, Spearman's correlation analysis, network analysis, Procrustes analysis, MaAsLin analysis, ERMANOVA analysis, random forest analysis of differential intestinal flora with differential metabolites between groups, and efficacy evaluation.

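### The random forest is given features already selected as different between groups and no held-out evaluation is described, so diagnostic performance will be biased upward if the same subjects serve both steps

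*Combined protocol and SAP*

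**What the plan says.** The second paragraph of section 2.5 of the combined protocol and SAP lists the methods for the omics data. The only predictive model in it is the last entry: "random forest analysis of differential intestinal flora with differential metabolites between groups, and efficacy evaluation". Nothing further is said about how the differential features are chosen, how the forest is fitted, or what the evaluation consists of.

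Section 2.2 gives the use intended for the results. The secondary outcome is to "provide new disease diagnostic strategies and progression risk assessment indicators for diabetic nephropathy", with early identification, diagnosis and prognosis as the applications.

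On the source of the data, section 2.1 says: "This study is an ongoing, single-center, cross-sectional observational clinical trial". It describes one recruitment into four groups. No section mentions a training and test split, cross-validation, a permutation check or an external validation cohort.

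**The concern.** A feature called differential between groups has been chosen with knowledge of the group labels. If that choice is made on all subjects, every subject has helped to pick the features, including any later held out to test the forest. Cross-validating the forest alone does not undo this, because the held-out subjects took part in the screen. Out-of-bag error has the same weakness. Chance differences that brought a feature through the screen are still present in the held-out subjects and count as predictive ability.

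The figure at stake is the accuracy reported for the diagnostic panel. A weak panel could be presented as a good one, and the report would give no means of telling how much of the figure came from the selection step.

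**Working it through.** **The plan's own figure.** The only design figure is the total of 720. It cannot be reproduced, because no effect size, power or target AUC accompanies it. It is used here only to set group sizes.

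**Inputs**
- Group size: "The total number of individuals proposed to be recruited in the four groups is 720". The split is not stated. 720/4 = 180 per group is assumed, with 90 per group as a sensitivity case.
- Screening threshold: "For other significance tests, an alpha level of 0.05 was used". That sentence is in the paragraph on clinical indicators. No threshold or multiplicity rule is given for the omics features, so an uncorrected 0.05 screen is an assumption.
- Screening test: "a Mann-Whitney rank-sum test (U test) was used for comparison between two groups", from the same paragraph. Its use as the omics screen is an assumption. Two-sided testing is stated only for the preliminary checks ("A two-sided test was employed for the normality test and variance chi-square test, with an alpha level of 0.1") and is also assumed.
- Number of candidate features, m: not stated. Section 2.4.2 names the platforms (16S rDNA, and "metagenomic Next Generation Sequencing, Non-targeted and targeted Metabolomics technology detection"). Values from 200 to 3000 are assumed.

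**Step 1. False selections when no marker is real.** The expected number is m × 0.05, which is 15, 50 and 150 for m = 300, 1000 and 3000. With independent features, the chance of at least one is 1 − 0.95^m, above 0.999 in each case.

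**Step 2. Effect on AUC when no marker is real.** Independent normal features, 200-tree forest, 5 folds, 8 replicates per row; the true AUC is 0.50. Entries are means, with the range over replicates in brackets.

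| Per group | m | Features selected | Same subjects | CV after screening all subjects | Screen inside each fold | New subjects |
|---|---|---|---|---|---|---|
| 180 | 300 | 18.25 | 1.000 | 0.674 (0.631–0.744) | 0.492 | 0.505 |
| 180 | 1000 | 51.625 | 1.000 | 0.780 (0.762–0.804) | 0.530 | 0.498 |
| 180 | 3000 | 146.75 | 1.000 | 0.875 (0.822–0.913) | 0.514 | 0.503 |
| 90 | 300 | 18.25 | 1.000 | 0.748 (0.670–0.805) | 0.517 | 0.506 |
| 90 | 1000 | 48.125 | 1.000 | 0.839 (0.786–0.910) | 0.497 | 0.530 |
| 90 | 3000 | 152.0 | 1.000 | 0.936 (0.896–0.961) | 0.508 | 0.501 |

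Two further sets of runs at 180 per group and m = 1000 gave 0.79 (8 replicates) and 0.76 (12 replicates) for CV after the screen, against 0.54 and 0.47 with the screen inside the folds. With fewer candidates the bias is smaller: 0.61 for m = 200 and 0.71 for m = 500, against 0.49 in both cases with the screen inside the folds. With features correlated 0.5 in blocks of 20 and m = 1000, CV after the screen gave 0.69, the screen inside the folds 0.48, and new subjects 0.50.

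**Step 3. When some markers are real.** 180 per group, m = 1000, 20 real markers, uncorrected 0.05 screen.

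| Shift per marker | Features | CV after screen | New subjects | Overstatement |
|---|---|---|---|---|
| 0.25 SD | independent | 0.80 | 0.61 | 0.19 |
| 0.25 SD | correlated blocks | 0.75 | 0.61 | 0.14 |
| 0.3 SD | independent | 0.85 | 0.68 | 0.17 |
| 0.5 SD | independent | 0.93 | 0.88 | 0.05 |

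For both 0.25 SD rows, the screen inside the folds gave 0.58, slightly below the new-subject value.

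**Step 4. If the screen used Benjamini-Hochberg control at 5%.** With no real marker, the mean number selected was 0 to 0.125 features, and AUC was 0.50 in both CV and new subjects. With real markers, CV after the screen against new subjects was:
- 0.25 SD, independent: 0.57 v 0.54, a gap of 0.03
- 0.25 SD, correlated blocks: 0.53 v 0.52, a gap of 0.01
- 0.3 SD: 0.62 v 0.59, a gap of 0.03
- 0.5 SD: 0.900 v 0.898, a gap of 0.002

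**Precision.** With 8 to 12 replicates, the null means for the screen inside the folds ran from 0.47 to 0.54 around a truth of 0.50. The inflation in Step 2 and the weak-marker gaps in Step 3 (0.14 to 0.19) are well beyond that scatter. The gaps in Step 4 are not; they show that the remaining bias is small there but do not fix its size.

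**The case against.** The strongest reply is that the plan states no order of work. The sentence is a list of techniques under the label of integrated correlation analysis. Its closing words on efficacy have no stated object and may be a loose translation. AUC, sensitivity and specificity appear nowhere in the document. The forest might be meant only to rank features or to relate flora to metabolites, with no claim about accuracy.

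Much of this stands. A reader might infer that the plan openly prescribes selecting, fitting and evaluating in the same subjects. It does not: the sequence, the shared subjects and the diagnostic meaning of the evaluation are all inferred. The inference is still the natural one. The text itself calls the inputs differential between groups, only one cohort exists, no safeguard is mentioned, and an observational study has no treatment whose efficacy could be evaluated.

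A second reply is that the size comes from a screen the plan never specifies for omics data. That also stands. The 0.05 threshold is borrowed from the clinical-indicator paragraph, and the feature counts, normality and independence are assumed. Correlation reduces the bias without removing it.

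A third reply is that this is multiplicity under another name. That is partly right. With false discovery rate control the null case almost disappears and the rest shrinks, so the point cannot be counted as wholly separate. It does not reduce to multiplicity, however: with real markers present, the reported accuracy was still overstated under the uncorrected screen.

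**Conclusion.** The concern holds in conditional form. If selection and evaluation share subjects and the evaluation is of diagnostic performance, the reported figure will be biased upward, and cross-validating the forest alone will not prevent it. With an uncorrected 0.05 screen, 180 per group and 1000 independent null features, AUC is about 0.76 to 0.79 instead of 0.50, or about 0.69 with block correlation. Weak real markers (0.25 SD) are overstated by about 0.14 to 0.19; stronger ones, at 0.5 SD, by about 0.05.

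A reader might go further and conclude that the panel will look good even when no marker is real. The document does not support that as a certainty: it requires an uncorrected screen, and the plan leaves the omics screening rule open.

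Nor is this a defect that undermines the study. It bears on a secondary aim of a cross-sectional study. Identifying candidate markers, the primary outcome, does not depend on the classifier's accuracy, and the problem can be cured at analysis with the same data. It should be fixed because the fix is cheap and the diagnostic claim is hard to interpret without it.

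**What to change.** Add to section 2.5 that feature screening, transformation and tuning are repeated inside each training fold (nested cross-validation), and that AUC with its confidence interval is computed only from predictions for subjects not used in any of those steps. State the omics screening rule and its multiplicity control in the same place, and say what the efficacy evaluation measures.

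An alternative is to set aside a fixed random share, for example 30% stratified by group, before any differential analysis and to report performance on it once.

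The nested version costs a few sentences, more computing time and a less favourable AUC; it needs no further subjects or samples. The hold-out version also leaves fewer subjects for discovery. Because section 2.1 describes the study as still under way, either can be written in before the analysis.

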## 3 Discussion

DKD is a common complication in the late stage of diabetes. What's more, it's a common cause of renal failure. By introducing the factors of gut microbiota and metabolites through multi-omics techniques, we conduct an analysis on the correlation of the onset of diabetic kidney disease to look for marker microbiota or metabolites and find relevant risk factors. This not only helps to explore the pathogenesis of DKD, but also provides a scientific basis for the early diagnosis, prevention and treatment of DKD. Even it is beneficial for delaying the progression of the disease, for drug research and development, and for changing potential treatment

strategies in the follow-up.

